5.2.7 Concomitant Medications and Non-drug Therapies

Concomitant medication is defined as prescribed or over-the-counter medications used during the study (e.g., either started prior to the study and continued on the study or started on or after the first dose of study drug). If a medication had a missing start date and a missing end date, or had a missing start date and an end date which was after the first day the subject was on study drug, or a start date which was after the date of the first day the subject was on study drug, the medication is considered concomitant. When partial concomitant medication start or end date exists, before determining whether concomitant or not, the following imputation rules are applied.

Partial start dates:

If day is missing (only month and year are present)

- If year and month are same as treatment start date then assign the day of treatment start date to the partial date
- Otherwise assign the day to '01'

If only year is present

- If year is same as treatment start date then assign the month and day of the treatment start date to the partial date
- Otherwise assign the month and day to 'January-01'

Partial end dates:

If day is missing (only month and year are present)

- If year and month are same as the year and month of study end date then assign the day of the study end date to the partial date
- If year and month are prior to the year and month of study end date then assign the last day of the month (28, 29, 30 or 31)

If only year is present

- If year is same as the year of study end date then assign the month and day of the study end date to the partial date
- If year is prior to the year of study end date then assign 'December-31' to the partial date.

If the study is ongoing and study end date is not available then the cut-off date will be used in the place of study end date

The WHO dictionary will be used for coding concomitant medication. MedDRA is used for coding concomitant non-drug therapies.

CONFIDENTIAL

The information contained herein may not be used, disclosed, or published without the written consent of
 Biogen Idec MA Inc.

	Protocol 109MS310 An Open-Label Study to Assess the Effects of BG00012 on Lymphocyte Subsets in Subjects With RRMS	Final Version 1.0
---	---	--------------------------

The number and percentage of subjects taking concomitant medication, concomitant MS medication, and receiving non-drug treatments will be summarized. Concomitant medication and non-drug concomitant medication will be listed.

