5.4.1 Adverse Events

AEs will be coded using MedDRA version of 19.1 or later. Only treatment-emergent AEs will be analyzed. A treatment-emergent AE is defined as any AE that has an *onset* date and time that is *on or after* the date of the first dose of study treatment, or that has *worsened after* the date of the first dose of study treatment. In the case of a worsening AE, the AE is supposed to be recorded as a new event with an onset date after first dose of study drug. Therefore, all treatment emergent AEs will be captured as AEs that have an onset date that is on or after date of first dose of study drug.

If an AE had a missing onset date and a missing resolution date, or had a missing onset date and a resolution date which was after the first day the subject was on study drug, or an onset date which was after the date of the first day the subject was on study drug, the event is considered treatment emergent. If the onset date of the AE was the same as date of the first day the subject took study drug the event is considered treatment-emergent. When partial AE start or end date exists, before determining whether treatment-emergent or not, the following imputation rules are applied.

Partial start dates:

If day is missing (only month and year are present)

- If year and month are same as treatment start date then assign the day of treatment start date to the partial date
- Otherwise assign the day to '01'

If only year is present

- If year is same as treatment start date then assign the month and day of the treatment start date to the partial date
- Otherwise assign the month and day to 'January-01'

Partial end dates:

If day is missing (only month and year are present)

- If year and month are same as the year and month of study end date then assign the day of the study end date to the partial date
- If year and month are prior to the year and month of study end date then assign the last day of the month (28, 29, 30 or 31)

If only year is present

CONFIDENTIAL

The information contained herein may not be used, disclosed, or published without the written consent of Biogen Idec MA Inc.

	Protocol 109MS310 An Open-Label Study to Assess the Effects of BG00012 on Lymphocyte Subsets in Subjects With RRMS	Final Version 1.0
---	---	--------------------------

- If year is same as the year of study end date then assign the month and day of the study end date to the partial date

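### The partial-start-date rule in SAP 5.4.1 and 5.2.7 ignores a known end date, so an SAE that resolved before first dose can be classed as treatment-emergent

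*SAP*

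**What the plan says.** SAP 5.2.7 (concomitant medications) gives two rules for partial start dates. When only the day is missing: "If year and month are same as treatment start date then assign the day of treatment start date to the partial date". When only the year is known: "If year is same as treatment start date then assign the month and day of the treatment start date to the partial date". If the known parts do not match the first dose, the first day of the known month or year is used. The order of steps is explicit: "before determining whether concomitant or not, the following imputation rules are applied". SAP 5.4.1 (adverse events) repeats both rules and the same order for AE onset dates.

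Neither section makes these rules depend on the end date. For a wholly missing start, both do. In 5.2.7 such a medication counts if it "had a missing start date and an end date which was after the first day the subject was on study drug" or if the end date is missing too; 5.4.1 has the parallel condition on the resolution date.

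For AEs the boundary case is settled. "If the onset date of the AE was the same as date of the first day the subject took study drug", the event is treatment-emergent, and the section adds that treatment-emergent events are identified by an onset on or after first dose.

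For medications the boundary case is not settled. The definition describes use during the study and gives as examples drugs "either started prior to the study and continued on the study or started on or after the first dose of study drug". The next sentence lists the qualifying conditions and ends "or a start date which was after the date of the first day the subject was on study drug, the medication is considered concomitant".

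Three protocol sections matter here. Section 15.3.1 records AEs from first dose. Section 15.3.2 records SAEs from signing of consent. Section 11.6.1 counts as concomitant any therapy given from the Screening Visit to the last study visit.

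**The concern.** Moving an uncertain start to the first-dose date is a reasonable conservative choice when the record could belong to either side of first dose. A known end date before first dose removes that uncertainty. The rule still assigns the first-dose date, so the record starts after it ended.

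A record with part of its start date is thus handled less accurately than one with none, because only the wholly missing case is checked against the end date. That looks like an omission rather than a deliberate choice.

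What is at stake is the treatment-emergent SAE table, which could attribute to the treatment period an event that began and ended before any BG00012 was taken. For medications, the derived dataset would hold impossible date pairs, and two programmers could classify the same record differently.

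**Working it through.** The plan states no figure on this point, so there is nothing to reproduce. The check applies the written rules to test records.

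**Inputs.** The imputation and classification rules come from SAP 5.2.7 and 5.4.1, the recording windows from protocol 15.3.1 and 15.3.2, and the screening window (up to 28 days) from protocol 7.2.1. The first-dose date, 15 Sep 2016, and all record dates are assumed.

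**Formula.** Duration = end date − imputed start + 1. A value of zero or less means that the imputed start is later than the end.

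| Record | Recorded start | Recorded end | Imputed start | Duration (days) | Class as written |
|---|---|---|---|---|---|
| SAE A | Sep 2016 | 10 Sep 2016 | 15 Sep 2016 | −4 | treatment-emergent |
| SAE B | 2016 | 30 Aug 2016 | 15 Sep 2016 | −15 | treatment-emergent |
| Drug C | Sep 2016 | 5 Sep 2016 | 15 Sep 2016 | −9 | depends on sentence used |
| Drug D | 2016 | 31 Mar 2016 | 15 Sep 2016 | −167 | depends on sentence used |
| Drug E (control) | Aug 2016 | 20 Aug 2016 | 1 Aug 2016 | 20 | not concomitant |
| Drug F (control) | 2015 | 31 Mar 2016 | 1 Jan 2015 | 456 | not concomitant |

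For example, SAE A: 10 − 15 + 1 = −4. Both SAEs fall within the 28 days before dosing, so they could have occurred after consent and been recorded. The last column uses the SAP definitions only.

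**Drugs C and D.** An imputed start equal to the first-dose date satisfies the example in the definition, which includes that date. It fails the qualifying sentence, which requires a later date. That sentence cannot be the whole rule: read alone, it would also leave out drugs that truly began on Day 1, and drugs with a known earlier start that continued on study. So the SAP text does not decide the class. Protocol 11.6.1 adds a third answer. Drug C, stopped 10 days before first dose, is concomitant under the protocol if Screening had taken place by then. Drug D, stopped 168 days before, lies outside the 28-day screening window and is not.

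**With an end-date guard** (if the recorded end is before the imputed start, use the first day of the known month or year):

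- SAE A: onset 1 Sep 2016, not treatment-emergent.
- SAE B: onset 1 Jan 2016, not treatment-emergent.
- Drug C: start 1 Sep 2016. Drug D: start 1 Jan 2016. Neither is concomitant under the SAP definition.
- Controls E and F: unchanged.

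**Reach of the day-missing rule.** If first dose falls on day d of a month, min(d − 1, 28) of the preceding 28 days share that month. Assuming first doses spread evenly over the 366 days of 2016, the sum is 7 × 462 + 4 × 434 + 406 = 5,376 days. The mean is 5,376/366 = 14.7 of 28 days, or 52%, with a range of 0% to 100%. This is the share of pre-dose days on which the rule could act, not a rate of misclassified records.

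**The case against.** The best case against the point is that it is remote and harmless. A misclassified SAE must begin and resolve between consent and first dose, about 28 days, in a subject who is then dosed, with a partial onset but a usable resolution date. The protocol requires SAEs to be reported within 24 hours of site awareness (15.3.3) and makes the investigator responsible for onset and resolution dates (15.6.1). SAEs are also listed individually, so an impossible date pair would be visible. The study has one arm, its safety analysis is descriptive, and the error leads to over-counting, so it hides no event. All of this stands and limits the size. It does not make the rule correct.

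A reader might go further and infer that every drug stopped before Day 1 with a matching partial start is wrongly counted as concomitant, so that the tables overstate use of other MS drugs or steroids on treatment. The documents do not support that. The phrase that includes the first-dose date is an example under use during the study, and the qualifying sentence would exclude the imputed record. Under protocol 11.6.1, a drug stopped between Screening and Day 1, such as a previous MS therapy given up at entry, is properly concomitant. The SAP summarizes prior MS treatment separately (5.2.3), and the documents do not show that drugs stopped before Screening reach the concomitant medication data.

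**Conclusion.** The point holds for adverse events. As written, SAP 5.4.1 classes as treatment-emergent an SAE known to have resolved before first dose, if its partial onset matches the first-dose month and year, or the year alone. In practice this concerns SAEs only, because other AEs are recorded from first dose. It assumes that pre-dose SAEs on the SAE form enter the analysis data and that the rule is programmed literally.

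For medications the supported conclusion is narrower: the rule produces a start later than the stop, and the SAP then does not say clearly which class applies.

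The number of affected records is not in the documents. It is probably very small, above all for SAEs. Medication status and AE classification do not enter the primary or secondary models (SAP 5.3.1 and 5.3.2), so the effect stays within descriptive safety and medication tables. This is a minor correction, worth making because it is cheap and the error would fall in an SAE table.

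**What to change.** In both SAP 5.2.7 and 5.4.1, add: a partial start that matches the first-dose month and year, or the year alone, is set to the first-dose date only if the end date, after its own imputation, is missing, ongoing, or on or after first dose. Otherwise the first day of the known month or year is used, and the imputed start may not be later than the end.

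In 5.4.1, also state that an event resolved before first dose is not treatment-emergent.

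In 5.2.7, do not add a blanket rule that a drug stopped before first dose is not concomitant. That would contradict protocol 11.6.1 for drugs stopped between Screening and Day 1, even with complete dates. Instead:

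- make the definition and the qualifying sentence agree on a start that falls on the first-dose date;
- reconcile the SAP definition with the protocol's, which begins at Screening, and record any intended departure in SAP 5.7.

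The guard costs a sentence or two in two sections and about one line of code in each derivation. Reconciling the medication definition needs a decision by the sponsor and may move some screening-period drugs into or out of the table. No new data are needed.

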5.3 Pharmacodynamics

The pharmacodynamic analysis will be based on data from the pharmacodynamic population as defined in [Section 5.1](#). The pharmacodynamic data includes the lymphocyte subsets, ALC, and isotypes (including IgA, IgM, IgG and IgG subclasses). A listing of reportable lymphocyte subset parameters are available in [Appendix 1](#). The lymphocyte subsets are categorized into the following eight groups:

- TBNK lymphocyte subsets
- T cell subsets
- B cell subsets
- Myeloid and NK cell subsets
- Intracellular T cell cytokines
- VLA-4/LFA-1 expression
- [REDACTED]
- [REDACTED]

Statistical analyses will be [REDACTED] and descriptive in nature, with appropriate measures of precision provided where applicable.

5.3.1 Analysis of the Primary Endpoint

The primary endpoints are the changes in lymphocyte subset counts for up to 48 weeks. The actual value, change and percent change from baseline in count and percent for each lymphocyte subset will be descriptively summarized at each applicable visit. Graphical display of median (Q1-25 percentile/Q3-75 percentile) of actual value and percent change from baseline in count and percent for each lymphocyte subset over time will also be presented. The Wilcoxon signed rank test will be used to test if the change and percent change from baseline in count and percent for each lymphocyte subset is different from zero. Listings of lymphocyte subsets will also be presented.

Furthermore, the primary endpoints will be summarized in various ALC subgroups to evaluate the nature of change in each subset in relation to the change in ALC.

ALC subgroups of interest include (1) subjects who have all ALC values \geq LLN ($0.91 \times 10^9/L$) up to Week 48, and (2) subjects who have at least 1 ALC value $<$ LLN over 48 weeks. A mixed model for repeated measures (MMRM) will be used to estimate the difference between ALC subgroups at each post-baseline visit up to Week 48. The model will be fitted with the change from baseline in count up to Week 48 for each of the TBNK lymphocyte subset as the dependent variable and will include ALC subgroup (all ALC values

CONFIDENTIAL

The information contained herein may not be used, disclosed, or published without the written consent of Biogen Idec MA Inc.

	Protocol 109MS310 An Open-Label Study to Assess the Effects of BG00012 on Lymphocyte Subsets in Subjects With RRMS	Final Version 1.0
---	---	--------------------------

\geq LLN up to Week 48; at least 1 ALC value $<$ LLN over 48 weeks), visit, corresponding Baseline counts, age, gender, and ALC subgroup-by-visit interaction as fixed effects. An unstructured variance-covariance matrix structure will be used in the MMRM model. Least squares (LS) mean, standard error, LS mean difference, 2-sided 95% confidence intervals (CIs) and p-values will be reported. Before the MMRM analysis, appropriate transformation may be performed based on the distribution of each TBNK lymphocyte subset parameter. The same analysis may be applied to other subsets.

Additional subgroups based on ALC values over time are defined:

- 1) ALC $< 0.5 \times 10^9/L$ for ≥ 6 months (24 weeks);
- 2) $0.5 \times 10^9/L \leq ALC < 0.8 \times 10^9/L$ for ≥ 6 months (excluding $< 0.5 \times 10^9/L$ for ≥ 6 months);
- 3) $<$ LLN any time (excluding $< 0.8 \times 10^9/L$ for ≥ 6 months);
- 4) ALC always \geq LLN.

Summary of actual value, change and percent change from baseline in count and percent for each lymphocyte subset will be presented by the ALC subgroups defined above.

The following subgroups analyses based on ALC during the first 48 weeks will be performed:

- 1) At least 2 ALC values $<$ LLN in the first 48 weeks;
- 2) Always \geq LLN or with one ALC $<$ LLN in the first 48 weeks

Additionally subgroups analyses based on baseline ALC quartiles will also be explored. The same descriptive summary on these subgroups will be applied to the count and percent for the TBNK lymphocyte subsets and may be applied to other subsets. Additional subgroups of interest may also be explored.

The correlation between TBNK actual value and ALC will be summarized by visit and also presented as plots.

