4 SAMPLE SIZE JUSTIFICATION

The sample size for this study is not based on formal hypothesis testing but on the precision of the estimation of the primary endpoints and the ratios between various ALC subgroups.

For example, the Phase 2 and 3 controlled and uncontrolled efficacy and safety studies in MS, based on data available as of May 2014 from 2470 subjects with at least 1 post-Baseline value from the interim analysis of the Integrated Summary of Safety of Tecfidera, showed that 76% of subjects had all ALC values \geq LLN and 24% had at least 1 ALC value $<$ LLN up to Week 48. Assuming the same proportion of subjects in this study will have 1 or more ALC values $<$ LLN, it is expected that approximately 137 subjects will have all ALC values \geq LLN and approximately 43 subjects will have at least 1 ALC value $<$ LLN at Week 48, based on a total of 180 evaluable subjects at Week 48. With this sample size, the 90% CIs for the ratio of the 2 subgroups for the change from Baseline at Week 48 in lymphocyte subsets are illustrated below using the scenario of a true ratio of 0.8 (20% decrease) and 0.7 (30% decrease), respectively. When assessing lymphocyte subsets between subjects with at least 2 ALC values $<$ LLN up to the first 48 weeks of treatment versus subjects who have all ALC values \geq LLN throughout the study, the 90% CIs of the ratio would be wider, as historical data suggest that 16% of the patients treated with Tecfidera may have 2 or more ALC values $<$ LLN during the first 48 weeks of treatment.

To allow for a 10% discontinuation rate, a total of 200 subjects are planned for enrollment.

Table 3: Sample Size Calculations

Primary Endpoints	SD ^{a)}	Ratio	90% CI for the Ratio Based on N = 180	
			Subjects With At Least 1 ALC $<$ LLN ^{b)} vs. Subjects With All ALC \geq LLN ^{b)}	Subjects With At Least 2 ALC $<$ LLN ^{b)} vs. Subjects With All ALC \geq LLN ^{b)}
	0.32	0.8	0.73, 0.88	0.71, 0.90

CONFIDENTIAL

The information contained herein may not be used, disclosed, or published without the written consent of Biogen Idec MA Inc.

biogen idec	Protocol 109MS310 An Open-Label Study to Assess the Effects of BG00012 on Lymphocyte Subsets in Subjects With RRMS	Final Version 1.0
--------------------	---	--------------------------

Primary Endpoints	SD^{a)}	Ratio	90% CI for the Ratio Based on N = 180	

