			Subjects With At Least 1 ALC <LLN^{b)} vs. Subjects With All ALC ≥LLN^{b)}	Subjects With At Least 2 ALC <LLN^{b)} vs. Subjects With All ALC ≥LLN^{b)}
CD4 T cell count		0.7	0.63, 0.77	0.63, 0.78
CD8 T cell count	0.35	0.8	0.72, 0.89	0.71, 0.91
		0.7	0.63, 0.78	0.62, 0.79
CD56 ^{bright} NK cell count	0.57	0.8	0.68, 0.95	0.65, 0.98
		0.7	0.59, 0.83	0.57, 0.86
T _{reg} count	0.95	0.8	0.60, 1.07	0.57, 1.12
		0.7	0.52, 0.93	0.50, 0.98

ALC = absolute lymphocyte count; CD = cluster of differentiation; CI = confidence interval; LLN = lower limit of normal; NK = natural killer; SD = standard deviation; T_{reg} = T regulatory; vs. = versus.

^{a)} Common standard deviation for the log-transformed change from Baseline.

^{b)} Up to Week 48.

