5 STATISTICAL ANALYSIS METHODS

5.1 General consideration

The statistical software, SAS[®], will be used for all summaries and statistical analyses.

This study only includes a single arm. In general, statistical analyses will be descriptive in nature with appropriate measures of variation provided where applicable. For continuous endpoints, number of subjects in the analysis population, number of subjects with non-missing observations, mean, standard deviation (SD), median, minimum and maximum will be reported. For categorical endpoints, number of subjects in the analysis population, number with non-missing observations, and the percent of those with data in each category will be summarized.

Several analysis populations are defined for different analysis purposes in this study. An overview of these analysis populations will be summarized.

- Pharmacodynamic Population - it is defined as all subjects who receive at least 1 dose of study treatment and have at least 1 pharmacodynamic measurement after Baseline.

CONFIDENTIAL

The information contained herein may not be used, disclosed, or published without the written consent of Biogen Idec MA Inc.

	Protocol 109MS310 An Open-Label Study to Assess the Effects of BG00012 on Lymphocyte Subsets in Subjects With RRMS	Final Version 1.0
---	---	--------------------------

- Safety Population – it is defined as all subjects who receive at least 1 dose of study treatment.

- [REDACTED]

[REDACTED]

In general, for data that are summarized by visit, any early withdrawal, unscheduled or scheduled visits will be assigned to an appropriate scheduled visit by using a mid-point of the two visits windowing scheme. The date of first dose will be the reference point. The detailed windowing rules for lymphocyte subsets, hematology, blood chemistry and vital signs are available in [Appendix 2](#). After windowing, if there is only 1 record in the visit window, then this record will be selected; if there are multiple records falling into the same visit window with different distance from the target day then select the one closest to the target day; if there are 2 visits with the same distance from the target day, but one is before the target day and the other is after the target day, then select the later one; for laboratory test, if more than one observation falls in the same distance from the target regular scheduled visit day, the mean observation will be calculated and used in the summary statistics and analyses.

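### The mean and signed rank test of percent change depend on a subset's variability: a 30% geometric fall has an expected mean of -26% for CD4 but +10% for Treg

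*SAP*

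**What the plan says.** SAP 5.3.1 applies to every subset: "change and percent change from baseline in count and percent for each lymphocyte subset will be descriptively summarized". What a descriptive summary contains is set in SAP 5.1 for all continuous endpoints: "mean, standard deviation (SD), median, minimum and maximum will be reported". No geometric mean or ratio to baseline is planned for the tables. SAP 5.3.1 also plots the median with quartiles for the subsets, and it tests both change and percent change against zero with the Wilcoxon signed rank test.

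The sample size section (SAP section 4; Protocol 16.7) works on a different scale. It considers a "true ratio of 0.8 (20% decrease) and 0.7 (30% decrease), respectively", and its Table 3 SDs are labelled "Common standard deviation for the log-transformed change from Baseline". The four SDs are 0.32 (CD4), 0.35 (CD8), 0.57 (CD56bright NK) and 0.95 (Treg).

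The mixed model, with a transformation that may be applied beforehand, is committed only for the TBNK subsets and is optional for the rest. Appendix 1 lists regulatory T cells under T cell subsets and CD56bright cells under myeloid and NK cell subsets, so neither has a committed model.

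**The concern.** Percent change cannot go below -100% but has no upper limit, so its distribution has a long right tail when log change is roughly symmetric. The arithmetic mean then lies above the median by an amount that grows with the spread of log change. Two subsets with the same proportional fall would show different mean percent changes simply because one is more variable. A reader comparing subsets down that column could take a variable subset as spared, or even increased, and a less variable one as depleted. The study asks how each subset changes in relation to ALC, so comparability across subsets matters.

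The signed rank test looks like a safeguard, but it relies on symmetry about the null value. Skewed percent changes violate that even when the median change is zero.

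**Working it through.** **1. Inputs.** From SAP section 4: SDs 0.32, 0.35, 0.57 and 0.95; illustrative ratios 0.8 and 0.7; 90% intervals; "based on a total of 180 evaluable subjects at Week 48". The split is 76% and 24%, which gives 0.76 × 180 ≈ 137 and 0.24 × 180 ≈ 43. For at least two low ALC values, 0.16 × 180 ≈ 29.

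**2. Confirm the scale by reproducing Table 3.** Interval = ratio × exp(±1.645 × SD × √(1/43 + 1/137)), where the square root is 0.1748.

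- CD4 at 0.8: 1.645 × 0.32 × 0.1748 = 0.092, giving 0.73 to 0.88, as printed.
- Treg at 0.8: 1.645 × 0.95 × 0.1748 = 0.273, giving 0.61 to 1.05. The printed row is "0.95 0.8 0.60, 1.07 0.57, 1.12", so the first interval there is slightly wider.
- All 32 limits in the table (both columns, with 29 against 137 in the second) agree within 0.02.
- For Treg at 0.7 (printed 0.52 to 0.93), base-10 logs would give 0.37 to 1.31 and base-2 logs 0.58 to 0.85. The SDs are therefore on the natural-log scale.

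**3. Expected mean percent change.** If log(follow-up/baseline) is normal with mean log(r) and SD s, the median percent change is r − 1 and the mean is r × exp(s²/2) − 1.

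| Subset | s | exp(s²/2) | Mean at r = 1.0 | Mean at r = 0.8 | Mean at r = 0.7 |
|---|---|---|---|---|---|
| CD4 | 0.32 | 1.053 | +5.3% | -15.8% | -26.3% |
| CD8 | 0.35 | 1.063 | +6.3% | -14.9% | -25.6% |
| CD56bright | 0.57 | 1.176 | +17.6% | -5.9% | -17.7% |
| Treg | 0.95 | 1.570 | +57.0% | +25.6% | +9.9% |

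The median is 0%, -20% and -30% respectively for every subset. At r = 0.7 the mean turns positive only if s exceeds √(2 × log(1/0.7)) = 0.845, which only Treg does.

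**4. Sampling variation for Treg at r = 0.7, N = 180 (simulation).** The mean percent change averages +10%, with 95% of trials between -8% and +31%, and is above zero in about 84%. The median averages about -30%, with 95% of trials between -41% and -17%.

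**5. The signed rank test (simulation, N = 180, lognormal change, two-sided 5%).**

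- With r = 1.0, the test on percent change declares an increase in about 16% of trials at SD 0.32, 36% to 38% at 0.57 and 66% at 0.95. On log ratios the figure is about 2%, as it should be for one tail.
- With a real Treg fall, the skewness works against detection. At r = 0.8 the test on percent change finds the fall in only about 8% to 9% of trials, and at r = 0.7 in about 61% to 63%.

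**The case against.** The best reply is that the plan already handles skewness.

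- **The median is present.** SAP 5.1 lists it beside the mean and does not rank the two, and the subset graphs use medians and quartiles. A reader might infer that a Treg fall would be hidden. The documents do not support that: a 30% geometric fall would show as a median of about -30% in the table and the figure. This stands and limits the consequence.
- **Percent change is not the primary endpoint.** The endpoint is change in counts, and the calculation above does not carry over to mean absolute change. This also stands.
- **The mean is a legitimate quantity.** The sample mean is unbiased for the population mean percent change; it is not the geometric change. A reader might attribute the gap to assay noise, but Table 3 does not separate assay error from real differences between subjects. The issue is therefore comparability across subsets and choice of summary, not estimator bias.
- **The 0.7 is borrowed.** Table 3's ratio compares ALC subgroups: "the 90% CIs for the ratio of the 2 subgroups for the change from Baseline at Week 48 in lymphocyte subsets". A 30% within-subject fall is an illustration, not a prediction by the plan.
- **A rank test is used.** This part of the reply fails, because the signed rank test needs symmetry and step 5 shows what happens without it. Protocol 16.2.2 plans no hypothesis testing, so the p-values should carry little weight, but SAP 5.3.1 does call for the test.

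A reader might also suspect that zero baselines, which make percent change undefined, remove many subjects for rare populations such as plasmablasts. The documents give no frequency of zeros, so only the missing rule can be noted.

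**Conclusion.** The point holds as a moderate one about the relative-change summary and its test. At a common geometric fall of 30%, expected mean percent change runs from -26.3% to +9.9% across the four Table 3 subsets. The distortion is about 4 points for CD4 and CD8 and about 12 for CD56bright; for Treg it is about 40 points, with a change of sign. Mean and median would then usually point in opposite directions for Treg, with no rule on which to interpret. The signed rank test of percent change has the same defect and can signal an increase where there is no geometric change. It matters most for Treg and CD56bright, because the SAP commits no model for them.

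The conclusion rests on three assumptions: log change is roughly normal, which Table 3 implies but does not state; the Table 3 SDs apply to within-subject change in this study; and about 180 subjects are evaluable. It does not support saying that the primary endpoint is compromised, that depletion would go unseen, or that every subset is materially affected.

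**What to change.** In SAP 5.3.1:

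- Report the geometric-mean ratio to baseline (back-transformed mean of the log ratios) with a confidence interval as the relative-change summary for subset counts, in place of the mean and SD of percent change. At minimum, add it beside them and name the geometric ratio and the median as the summaries to interpret.
- Keep the median and add Q1 and Q3 to the tables, to match the graphs.
- Apply the signed rank test to the log ratio instead of percent change.
- For any subset with zero counts, report median absolute change and the number of subjects with a zero baseline. A zero at follow-up also leaves the log ratio undefined, so the rule should cover it.

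The cost is SAP wording and table shells, with no new data. Dropping the mean of percent change loses direct comparability with earlier tables that used it; the minimum option avoids that loss.
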